Some payer and payment information is being collected to help gain insight into reimbursement of SRS/SBRT/SFRT treatment for different diagnoses by different health plans. Individual patient health plan numbers are *not* included in the database.

Patient email addresses may be collected by individual sites to allow patients to access the Patient Portal in order to view and complete select Quality of Life forms. If email addresses are collected for this purpose, these emails are only visible to the individual site and will be protected by the software application processes put in place by VisionTree.

All patient data will be de-identified prior to use for research and analysis. If and when comparisons of aggregate data are made, no specifically identified patient-to-patient, physician-to-physician or geographic comparisons of data will be performed.

11 Security

Participants will be required to enter a unique username and password to access the RSSearch Patient Registry. No sharing of usernames and passwords will be allowed.

If a clinical site determines they need written copies of RSSearch Data Collection Forms, these should be managed in accordance with data protection regulations by that clinical site.

12 Reporting

Participants may routinely access reports of their own individual center's data and are free to publish their own data at any time. The particular research and methods must be evaluated for scientific merit and ethical propriety by their own institutions. Publications or presentations that result from the RSSearch Registry should be acknowledged accordingly.

The RSSearch Registry Review Committee (RRRC) composed of SRS/SBRT/SFRT users may review and release de-identified aggregate data as deemed appropriate for publication. Any individual participating site may choose to have their data included or excluded in the released aggregate data, but because aggregate data will not contain any identifiers, either patient, physician or site, all participating sites will be encouraged to include their data to increase the value for educational purposes. Participating sites/clinicians and the RSS may submit requests for aggregate data for publication to the expert review panel. Please see Appendix D for details on aggregate reporting.

13 IRB/Ethics Review Committee Approval

IRB or Ethics Review Committee review and approval is required to participate in the RSSearch Registry (see Appendix A for review considerations).

Patient Informed Consent

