 - a. To match the various Treatment Planning System data
 - b. To assist in long term follow up at the participating site
 - c. For registry operations
4. Physician-specific data will only be available to the respective site.
5. The RSSearch® Patient Registry is being managed in a secure environment by VisionTree®, San Diego, CA, an independent developer of web-based registries.

19 Appendix D: Access to Data and Aggregate Reporting

Overview

This guideline provides information on the specific and accepted professional use of data and database-derived information of the RSSearch® Patient Registry.

Use of Data

Participants: RSSearch® Patient Registry “Participants” may consist solely of one or more physicians, physicists, nurses and site administrators, plus their hospital or center, at the physician’s election, who engage in the process of collecting clinical practice data and utilization of data-base derived information.

Participants may routinely access reports of their own individual center’s data and are free to publish their own data at any time. The particular research and methods must be evaluated for scientific merit and ethical propriety by their own Institutional Review Board or Ethic Review Committee.

Any individual participating site may choose to have their data included or excluded in the released aggregate data, but because aggregate raw data will not contain any identifiers, either patient, physician or site, all participating sites will be encouraged to include their data to increase the value for educational purposes. Participating sites/clinicians and the RSS may submit requests for aggregate data for publication for expert review panel.

Registry Administrator: The RSSearch® Patient Registry Administrators are the RSS employees, who are responsible for managing the development and maintenance of the registry. The responsibilities of the Administrators include:

- Oversee the management, development and maintenance of the database
- Providing participants with the most recent updated registry protocol, sample consent form and supporting materials for IRB, Ethics Review Committee or regulatory agency equivalent submission
- Acting as a liaison between the participants and the database vendor
- Creating and editing Data Collection Forms
- Notifying the database vendor of new participants or changes user access
- Coordinating database training

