- Create and distribute timely reports of limited aggregate data under advisement of the RRRC
- Review and process applications for access to aggregate data
- May create, distribute and report on aggregate data and Quality Assurance and Performance Improvement studies with prior approval by the RSSearch® Patient Registry Review Committee (RRRC)

The Administrator will have read only access to de-identified registry data. All physician and specific patient identifying information will be restricted and not visible to the Administrator.

Aggregate Data Reporting: The RSSearch® Registry Review Committee (RRRC) will periodically review opportunities for presenting topline aggregate data to all participants via the Registry.

Access to data for publication and presentation: Data entered into the registry is available for research and publications. Clinical research on aggregated data may be used to produce one or more of the following forms of reporting and dissemination of information: abstract, scientific meeting presentation,

RSSearch® Patient Registry Protocol

Version Date: 7/19/2022 Version 1.1

manuscript for publication in the medical literature. Patient identifying information will remain confidential.

All publications will include reference to all participating RSSearch® sites. Researchers will be provided assistance in getting permission to be named in a publication by the RSSearch Administrator.

RSSearch® Registry Review Committee (RRRC):

The RRRC consists of clinicians with extensive SRS and SBRT experience that have been selected by RSS Board of Directors. The RRRC evaluates the proposals based on originality, interest and benefit to the entire SRS and SBRT community and feasibility (as defined by availability of data in the aggregate database).

All persons interested in publishing RSSearch® aggregate data must submit their proposal for publication and request for data analyses to the RRRC using the RSSearch® Request For Use of Aggregate Data Form (see Attachment D.1). **The Radiosurgery Society®** will submit requests for aggregate data for publication to the RRRC. The RRRC will review individual applications for aggregate data release. There is no fee to submit an application for RRRC.

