As indicated above and throughout the document, no physician, patient, or site identifying information is available or will be made available in granted requests for aggregate data. Site identifying information will be provided to the Radiosurgery Society for purposes of aggregate study requests and for conducting quality assurance of the database.

RSSearch® Data Request Form for Use of Aggregate Data:

Eligibility Criteria for Participating Centers

(The RSS will not be held to below criteria)

- Enter > 50 patients into RSSearch® annually
- Principal Investigator must be an RSS member
- The RSS will not be held to this criterion

Submission Requirements

Please attach each of the following with your RSSearch® Request For Use of Aggregate Data Form:

- Copy of IRB approval letter for use of RSSearch® at your institution
- Curriculum vitae of the principal investigator
- The RSS will not be held to this criterion

General Information

Submit Appendix D: Access to Data and Aggregate Reporting to the RSS RSSearch Administrator at [contact] You will receive a letter regarding the status of your request within 30 business days. Requested custom aggregate data report will require a minimum of 2 weeks to generate.

Request For Use of Aggregate Data Form

Date of Submission (mm/dd/yy):	
Name of Organization:	
Project Title:	
Principal Investigator:	
Co-Investigators:	
Corresponding Contact Name:	
Contact Title:	
Contact Telephone Number:	
Contact E-mail Address:	
Contact Address: City, State, Zip:	

Project Description

Project Start Date (mm/dd/yy):	
Project End Date (mm/dd/yy):	
Type of Research Project:	 Prospective Study  Retrospective Analysis  Technical Study  Other
If "Other," please explain nature of project:	
What is the research question being asked?	
What is the background or rationale for the research question? (if needed, please attach as a separate page to application)	
Patient Inclusion/Exclusion Criteria:	

Data Requested

Description of patient population to be analyzed:	
Time frame to be studied:	
List exact data variables requested (i.e. pathology, treatment planning)	

information, outcome, reimbursement, etc.): If the request is not self-evident, write a summary of the request and/or instructions on data output (e.g., table specifications, sample tables).	
Deadline for receipt of data (mm/dd/yy):	

Data Use

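### Does giving site identity to the Society undo the assurance that released aggregate data carry no site identifiers?

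*Protocol*

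**What the plan says.** Section 12 (Reporting) gives each site a choice: "Any individual participating site may choose to have their data included or excluded in the released aggregate data". It then encourages inclusion "because aggregate data will not contain any identifiers, either patient, physician or site". Appendix D, under Use of Data, repeats this for raw aggregate data: "because aggregate raw data will not contain any identifiers, either patient, physician or site". Near the request form, Appendix D states the rule a third time: "no physician, patient, or site identifying information is available or will be made available in granted requests for aggregate data".

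The sentence directly after that third statement says that the Society will receive information identifying sites. It names two purposes: aggregate study requests and quality assurance of the database.

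The Society is also a requester. Section 12 says "Participating sites/clinicians and the RSS may submit requests for aggregate data for publication to the expert review panel", Appendix D has nearly the same sentence, and the paragraph on the Registry Review Committee says that the Society "will submit requests for aggregate data for publication to the RRRC". The registry Administrators are Society employees. They have read-only access to de-identified data, and Appendix D adds: "All physician and specific patient identifying information will be restricted and not visible to the Administrator". Site identity is not in that restriction.

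**The concern.** The assurance makes no exception by type of requester, and the protocol uses it as the reason why sites should not withhold their data. Section 5 requires each site to submit this protocol to its review board, so sites and boards rely on the wording. If the Society receives site identity for aggregate study requests, and some of those requests are its own, then one named requester might work with data that show which site each record came from. On that reading the assurance would be too broad.

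There is also a question for the analyst. A pooled analysis across centres often needs to group records by site. If access to site identity depends on who asks, so might the ability to allow for differences between sites. The documents also use two terms, identifiers in two places and identifying information in the third. They do not say whether a code that reveals nothing could accompany data released to an outside requester.

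**Working it through.** No arithmetic applies. The check sets the statements side by side and asks whether they can all be true.

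1. **What the assurance covers.** All three statements concern the content of aggregate data that are released or granted. The third covers every granted request without exception, so as worded it covers requests by the Society too.

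2. **What the next sentence covers.** It says what the Society receives. It does not say that a data set granted to the Society carries site identity. A registry holder can know which site entered which record while the analysis file omits it. Both sentences can therefore hold.

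3. **Whether an administrative purpose is plausible.** Several tasks in the protocol need site identity:
   - applying a site's choice to be left out of a release (section 12);
   - checking that a requesting centre enters more than 50 patients a year (Appendix D, eligibility criteria);
   - holding site agreements and approval documents (section 5);
   - telling the database vendor about new participants (Appendix D);
   - crediting all participating sites in publications and helping with permission to name them (Appendix D).

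4. **The Administrator restriction.** It lists physician and patient identity but not site identity. This agrees with the sentence that gives site identity to the Society, so it is not a separate gap.

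5. **The Society's exemptions.** Appendix D frees the Society from criteria on patient volume, membership, the approval letter and the curriculum vitae. None of these lifts the rule on identifiers, and the Society's requests still go to the Review Committee.

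6. **Outside requesters.** For them the third statement repeats the first two. There is no tension.

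7. **Codes.** The difference between identifiers and identifying information is ordinary variation in wording. Nothing bars a non-identifying code. Whether one accompanies an extract is a detail for the individual data request or a data-use agreement. The request form asks for exact variables and output instructions, and section 8 says the forms are linked electronically to patients, so grouping can be arranged when a project needs it.

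8. **Effect on results.** Section 7 says that the registry has no established endpoints. The protocol states no sample size, error rate or effect estimate that depends on who holds site identity. There is no figure to reproduce and none that would move.

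**The case for a change.** The strongest reply is that the Society is more than a data holder. Its employees process other parties' applications and, with Review Committee approval, may also create and report on aggregate data themselves. The protocol does not separate these two roles, and it does not say that site identity is removed when the Society is the requester. The administrative reading is sensible, but it is inferred from the tasks listed and not written down. This is also access wording that the protocol itself fixes, so an unseen statistical analysis plan would not be expected to settle it.

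That much stands: the purpose phrase admits two readings, and the protocol does not choose between them. It does not follow that the assurance fails for the Society's own requests, because that takes the wider reading as settled. Nor are sites and boards kept in the dark. The access is stated directly after the assurance, with its recipient and purposes, in the appendix to which section 12 refers. Boards see it because this protocol is what sites must submit.

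**Conclusion.** The concern identifies a real looseness of wording, but no contradiction and nothing that calls for a change to the plan. The size is nil in statistical terms: no bias, error rate, estimate or conclusion is affected under either reading. On the narrow reading the Society uses site identity to run the request process, and released data are as described. On the wide reading the Society's own analysts could also group by site, which would help a pooled analysis; the remaining question would be how fully sites were told, not whether results are valid.

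The conclusion rests on two assumptions. First, the rule on granted requests applies to the Society as to anyone else, as its wording implies. Second, the site agreements required by section 5, which are not shown, do not promise something different. If the sponsor revises Appendix D for other reasons, the purpose phrase could be made more exact, but this would only record what a careful reader already infers.
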